
Table 1. Justice-involved women's health risk, N=261	N (% or SD)
Cervical cancer risk	
No Pap test in past 3 years	59 (22.6)
Lifetime abnormal Pap test	126 (48.2)
Cervical cancer diagnosis	30 (11.4)
Breast cancer risk	
No mammogram for 50 or older (N=23) in past 2 years	11 (47.8)
Unintended pregnancy risk	
Lifetime unintended pregnancy	207 (79.3)
No past month birth control use (excluding hysterectomy)	76 (29.1)
Sexually transmitted infection risk	
Lifetime STI history	163 (62.4)
No condom use at last sex	196 (75.1)
Ever sold sex	91 (34.8)
Cross-cutting risk factors	
Past month tobacco use	205 (78.5)
Alcohol use problem	132 (50.5)
Past year drug dependence	163 (62.4)
Lifetime mental health diagnosis	191 (73.1)
Past year intimate partner violence	133 (50.9)
Uninsured	160 (61.3)
No primary care doctor	150 (57.4)
No medical home	70 (26.8)
Lifetime months incarcerated, Mean	24.2 (45.3)
Race/ethnic group with higher cancer mortality	
e.g. Black	83 (31.8)
e.g. Hispanic	21 (8.0)
Age, Mean	33.7 (±9.9)

Table 2. SHE-Women - A women's health literacy curriculum

Knowledge of cervical, breast cancer, birth control, and STIs	Beliefs about cervical, breast cancer, birth control, and STIs	Self-Efficacy for cervical, breast cancer, birth control, and STI screening	Confidence navigating health systems for screening and risk reduction
Female body anatomy Medical terminology How stuff works in the body, prevention, and cures Procedures Costs	Beliefs about disease Beliefs about screening Where you learned about sex/health/prevention? What do you share with kids, partners? Romantic/sexual relationship dynamics Experiences with providers Motivations for screening and prevention	What is self-efficacy? Do you know where to go for services/experiences at these places/barriers? Do romantic/sexual partners get in the way/help? How to get results? What makes it easy to get services? Drug use/ homelessness/ transportation/ financial/ other barriers – how to overcome?	Confidence navigating providers given long-term criminal justice involvement? Jail health care and services, trust, cost Outside of jail services, trust, cost, fears Insurance/no insurance Social support for health care seeking Coercion

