Aim 2 RCT settings will be various locations in the Kansas City metro: two urban city/county jails in Kansas City – one facility on the Missouri side of the state line, and one facility in Kansas. We will also recruit women in various community settings with the women having a release date of five years post incarceration. We will recruit women in social support centers, DV shelters, transitional living facilities and other community organizations where our population may frequent. Our goal is to work with women leaving jail or with recent criminal justice involvement using an electronic women's health literacy intervention modality; volunteer for the study; and do not exhibit psychological distress, which would prohibit informed consent. There are no age or medical study exclusions, since all women could potentially benefit for guidance on cervical, breast, unintended pregnancy, and STI screening. For recruitment in jails, we will work with discharge planners to recruit women scheduled to be released from jail. The jail staff will distribute hygiene packets to women as they are being released while introducing the program. Included in these packets, the women will see a business card with our picture and contact info so that if they are interested, they can call us. For sampling, on any given day, about 120 women are incarcerated in the KC, MO facility and 45 women are incarcerated in the KC, KS facility. In local community organizations, we will distribute our 'flyer' that will be placed in the organization, where the population frequents. We will recruit a convenience sample of N~260 women for the RCT, oversampling to account for attrition, with the goal of ending with N~200 women for the RCT. In our previous studies, we have found that in these facilities between 1-4 women are released each day, and that we were

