able to recruit about 50% of these women.^{3,4,9} Given the sample size of women being released each day, our ability to recruit, and staff schedules, we anticipate that it will take one year to recruit the RCT sample, though we are allowing for a two-year period in case we have challenges. To increase the sample size, respondent-driven sampling (RDS) will be used. The post-intervention survey will ask participants if they have friends who have been in jail or prison within the past 5 years and who would be interested in participating in this study. Participants will have friends contact the study team and can have up to 5 friends complete the baseline survey, earning \$20 for each completed baseline survey (with the potential to earn up to \$100). Sample seeds will be tracked in Redcap. Because of our relationship with our current population of women (participants in the parent SHE study), we have a unique opportunity to recruit women from our participants in our parent study. These women will receive the same incentive: up to \$100 for five friends who consent and complete a baseline survey.

Aim 3 settings will be in the community. We will track participants and interview key stakeholders in the community. All participants, regardless of intervention assignment, will be invited to utilize text messaging with a health educator and attend community sessions. The community sessions will be at two public libraries in neighborhoods where > 50% of participants live.¹⁸ Eligibility for participants will be enrolling in the Aim 2 RCT. Recruitment will be as follows: to assess perceptions of human interaction in intervention delivery, we will recruit for key stakeholder interviews five participants from intervention arm; five participants from control arm; and 10 participants who utilized text messaging with health educator or community sessions. We will ask the first participants we interview for Aim 2 follow-ups if they would like to be interviewed; if they say no, we will move on to the next participant we encounter in follow-up. Sampling will be purposive. We will track all participants in the RCT to assess intervention uptake. We will also choose 40 random participants to participate in the COVID-19 module interview. The participants will receive \$10 to complete a 20 minute interview. Data collection for this aim will occur throughout the study period, leaving sufficient time for more key stakeholder interviews if needed.

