Power. The sample size for the Aim 1 feasibility study is based on our original SHE study pilot and expanded to allow for rigorous testing and refining of modality.²⁶ The sample size of N~200 for the Aim 2 RCT was determined to provide satisfactory power ($\geq 80\%$) for this study in addressing the specific aims, which depends on the following parameters: number of participants (n), number of measurements (t=3 for health literacy for screening; t=4 for screening/risk reduction practices), effect size (f) as group difference in change, correlation between repeated measures (r), and attrition rate. The effect sizes estimated from the original SHE study were in the small to moderate range—for health literacy (8 domains), average $f=0.13$ at immediately post-intervention and 0.16 at 1-year post-intervention; $f=0.17$ for cervix screening and 0.12 for condom use during the last intercourse at 1-year post-intervention. Although effect sizes for breast cancer screening and STI screening are not available from the original SHE study, we expect similar, small to moderate effect sizes for these outcomes. Thus, we conservatively assumed the smallest observed effect size of $f=0.12$ for our power calculation. The correlations between repeated measures observed in the original SHE study were $r=0.46$ on average, with the range of 0.39-0.75 between baseline and immediately post-intervention and 0.25-0.61 between baseline and 1-year post-intervention. Power analysis of these data ($f=0.13$, $t=3$ or 4, $r=0.46$) and G*Power 3.1.9.2 indicated that a sample of 124 women will produce $\geq 80\%$ power for both health literacy (80%) and screening/risk reduction behaviors (85%). In our original SHE study, the 3-year follow-up rate was 85%. Conservatively assuming a high attrition rate up to 40%, we will recruit ~200 women at baseline to adequately power the SHE-Women study—i.e., maintain $\geq 80\%$ power even with a low follow-up rate as small as 60%. As

Table 4. Expected attrition over study period

	Aim 1 feasibility Target N~20	Aim 2 RCT Target N~200	Aim 3 (same as Aim 2)
Consent and baseline	20	260	--
Intervention initiation	15	220	--
Post-intervention	10	200	--
1 year follow-up	--	170	--
2-year follow-up	--	160	--
3-year follow-up	--	150	--

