- *Potential problems with delivery of intervention:* number of incorrect phone numbers, changed phone numbers; problems with Website described by participants and staff; description of level of annoyance with outreach messages through text, phone, and Facebook; number of participants re-incarcerated during intervention trial and, thus, resulted in non-completion; problems with chat feature with health educator
- *Modifications needed to maximize implementation:* suggestions from participants about improving multimedia electronic approaches; suggestions about improving real-time assessments of knowledge
- *Perception of human interaction in intervention:* positive and negative aspects of multimedia electronic educational interventions; benefits and disadvantages to offer of community-based sessions; perceived value of human face in video/audio intervention content; advantages/disadvantages of conversation during discharge planning session for control arm

Women's health literacy and screening/risk reduction outcomes are described in Table 5 below. Items will be adapted from scales listed in Table 5.

Table 5. Women's health literacy and screening/risk reduction outcomes and instruments	
Women's health literacy (Knowledge, beliefs, self-efficacy, confidence navigating systems)	Screening/ Risk reduction
Cervix literacy Pap knowledge scale ⁴⁶ Health belief model scale for cervical cancer and Pap smear test ⁴⁷ Self-efficacy for cancer screening scale ⁴⁸ Confidence navigating health systems scale (cervix, breast, birth control, STI) ⁴	Up-to-date Pap exam or HPV co-testing Abnormal Pap follow-up HINTS cervical cancer screening questions ⁴⁹ Original SHE HPV co-testing and abnormal Pap follow-up questions ⁴
Breast literacy Knowledge, beliefs, self-efficacy items from breast cancer literacy assessment ⁵⁰	Up-to-date screening mammography (biennial) for age 50+ HINTS breast cancer screening questions ⁴⁹
Birth control literacy Contraceptive knowledge assessment ⁵¹ Beliefs about acquisition and use of contraceptive items from self-efficacy scale ⁵²	Current use of hormonal or long-acting reversible birth control method, if no menopause or sterilization BRFSS birth control questions ⁵³
Sexually transmitted infection literacy STD knowledge questionnaire ⁵⁴ Multidimensional condom attitudes scale ⁵⁵ Condom self-efficacy scale ⁵⁶	Condom use at last sex STI treatment BRFSS condom use and STI treatment questions ⁵³

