Using quantitative data from the pilot trial of the SHE-Women text-Web intervention, we will conduct descriptive analysis and bivariate tests to explore women's health literacy (knowledge, beliefs, and self-efficacy) for screening related to cervical, breast cancer, birth control, and STIs (Aim 1). The results including effect sizes estimated for the outcome will be utilized for refinement of the intervention content and modality. To test the hypothesis that SHE-Women will be more effective than standard of care at improving outcomes (Aim 2), we will utilize mixed modeling techniques for repeated measures, separately for each outcome variable: health literacy for screening and screening/risk reduction practices. General/generalized models will evaluate the effects of the intervention by estimating overall group difference across measurements (i.e., group effect), change over time (i.e., time effect), and group difference in change (i.e., group-by-time interaction). In other words, we will evaluate whether the intervention vs. control group improves in outcomes over time. The models will account for the impacts of sociodemographic characteristics as well as other cross-cutting risk factors including tobacco use, alcohol use, criminal justice involvement, intimate partner violence, lack of continuous health care coverage or primary care contact, etc. (covariates), thereby providing unbiased estimates of the intervention effects. The models for screening/risk reduction behaviors will also consider knowledge about cervix cancer, breast cancer, birth control, or STI as an additional covariate for the respective outcome variable. Incorporating participant tracking data, descriptive analysis and bivariate tests will demonstrate the pattern and uptake of various intervention components as measured by number of participants who responded to text messages; clicks on the Website; interactive clicks on the Website, e.g. through real-time assessment of knowledge; time elapsed between text messages and Website clicks; number of outreach messages (through text, phone, or Facebook); Facebook posts/messages; chats with health educator; total minutes of contact through text, Web, chat, Facebook with each participant; and attendance at community sessions (Aim 3). General/generalized mixed modeling for repeated measures will assess the impacts of the uptake on each outcome variable of health literacy for screening and screening/risk reduction practices while controlling for the impact of sociodemographic characteristics and other risk factors. A proper covariance structure for repeated measures will be chosen for each outcome variable based on model fit (i.e., likelihood, Akaike Information Criterion, adjusted Bayesian Information Criterion). Statistical significance will be determined at 0.05 alpha level, and all analyses conducted using SAS 9.4⁵⁹

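### The power stated for screening and risk-reduction behaviors does not cover mammography, which is defined only for women aged 50 and over

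*Combined protocol and SAP*

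**What the plan says.** The Power section reports that 124 women give at least 80% "power for both health literacy (80%) and screening/risk reduction behaviors (85" per cent). It acknowledges that the earlier study supplied no effect size for breast cancer screening or STI screening, and brings them under the same calculation with the words "we expect similar, small to moderate effect sizes for these outcomes". The behavior effects it does have are "f=0.17$ for cervix screening and 0.12 for condom use" at one year.

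Table 5 gives the breast screening outcome as "Up-to-date screening mammography (biennial) for age 50" and over. The Data analysis section uses "mixed modeling techniques for repeated measures, separately for each outcome variable". On recruitment, the Settings, eligibility, recruitment, and sampling section says "There are no age or medical study exclusions" and adds "To increase the sample size, respondent-driven sampling (RDS) will be used"; it sets no quota by age. The only count of older women is in Table 1, for the earlier cohort of 261: "No mammogram for 50 or older (N=23) in past 2 years".

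The Power section also says that f=0.12 was assumed, and then prints f=0.13 among the inputs to the calculation.

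**The concern.** The 85% figure requires all 124 women to contribute to the outcome. Mammography is observed only in the part of the sample aged 50 and over, and because each outcome has its own model, the other outcomes lend it no information. The plan gives neither an expected number of eligible women nor a separate power figure.

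Breast cancer is one of the four target areas, and Table 3 plans manuscripts on screening and risk reduction. As the text stands, a null mammography result from a small number of women could be reported as coming from a trial with at least 80% power, and so be taken as evidence of no effect.

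**Working it through.** **Inputs.** From the Power section: N=124; t=3 measurements for literacy and t=4 for behaviors; average correlation r=0.46; f=0.12 (assumed) or 0.13 (printed); f=0.17 as the largest behavior effect reported. From Data analysis: alpha 0.05. From Table 3: two arms of about equal size. From Table 1: 23 of 261 women aged 50 or older.

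**Formula.** Repeated-measures test of the group-by-time interaction with two groups: noncentrality λ = f² × N × t / (1 − r). The univariate form (epsilon 1) uses df1 = t − 1 and df2 = (N − 2)(t − 1). The multivariate form uses the same λ and df1, with df2 = N − t. The plan does not say which G*Power option was used, so both are shown.

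**Step 1: the plan's own figures, N=124.**
- f=0.12, t=3: λ = 0.0144 × 124 × 3 / 0.54 = 9.92; power 80.7% (univariate), 80.2% (multivariate).
- f=0.12, t=4: λ = 0.0144 × 124 × 4 / 0.54 = 13.23; power 87.3%, 86.5%.
- f=0.13, t=3: λ = 11.64; power 86.9%, 86.4%.
- f=0.13, t=4: λ = 15.52; power 92.4%, 91.7%.

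The stated 80% and 85% agree closely with f=0.12. In the multivariate form, 124 is also the smallest even N that reaches 80% at t=3 (122 gives 79.5%).

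**Step 2: number eligible for mammography.** 23/261 = 8.8%, and 0.088 × 200 ≈ 18 women. Carrying this share over is an assumption. As a generous alternative, take 20% of 200 = 40 women.

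**Step 3: mammography power, t=4, r=0.46.** For 18 women at f=0.12, λ = 0.0144 × 18 × 4 / 0.54 = 1.92. The remaining cells follow in the same way (multivariate to univariate):

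| Eligible women | f=0.12 | f=0.13 | f=0.17 |
|---|---|---|---|
| 18 | 15.1-17.4% | 17.1-19.9% | 27.0-32.1% |
| 40 | 34.5-36.9% | 40.0-42.8% | 63.5-67.1% |

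**Step 4: what 80% would take.** At f=0.12, 104 (univariate) to 107 (multivariate) eligible women; at f=0.13, 89 to 92. That is about 45-54% of 200. With only 18 women, f would have to be about 0.30-0.33.

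**Step 5: a check for a yes/no outcome.** Steps 1 to 4 treat a binary outcome as continuous, as the plan does. For a single time point with Fisher's exact test, take 12/23 = 52% up to date in the control arm (Table 1: 23 − 11 = 12). The intervention rates are illustrative assumptions. Against 90%, power is 26% with 9 women per arm and 69% with 20 per arm. Against 75%, it is 9% and 23%.

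**The case against.** The Power section gives one figure for a class of behaviors and never prints a power for mammography itself. It is open about having no breast screening effect size. The 8.8% share comes from a jail cohort, whereas this trial adds community sites and respondent-driven sampling, so more older women may enrol. All of this stands, and it is why the 18 is labelled an assumption. It does not rescue the claim: breast screening is named when the shared effect size is justified, and no passage secures enough women aged 50 and over. The planned multiple imputation does not help either, because younger women are outside the outcome's definition and are not missing from it.

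A reader might infer more than the documents support, in four ways.
- *That mammography power is far below 80% at any plausible age share.* At the plan's own f=0.17, 40 women give 63-67%, which is short of 80% but not far below it.
- *That the trial as a whole is too small.* The stated inputs reproduce the stated power for outcomes measured in all women.
- *That those other outcomes are therefore secure.* The match holds at the average r=0.46. At r=0.25, the low end reported between baseline and one year, f=0.12 with 124 women gives 65-66% (t=3) and 72-73% (t=4).
- *That the two f values make the sample size untraceable.* Step 1 shows that it traces to f=0.12. The printed 0.13 is most likely a slip; the same paragraph gives 0.13 as the average literacy effect immediately after the intervention.

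**Conclusion.** The concern holds for mammography. A claim of at least 80% power (85% at N=124) cannot apply to an outcome restricted to women aged 50 and over when no number of such women is secured. At about 18 eligible women, power is roughly 15-20% at f=0.12-0.13 and 27-32% at f=0.17; at 40 eligible women it is about 35-43% and 63-67%. These figures rest on t=4, r=0.46, equal arms, a continuous-outcome approximation and an assumed age share. The conclusion is not sensitive to that share at the plan's assumed effect, since about half of the 200 women would have to be 50 or older to reach 80%.

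The f=0.12 versus f=0.13 discrepancy is a minor reporting matter. Neither part shows an error in the planned sample size.

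**What to change.** In the Power section:
- Limit the statement of at least 80% power to outcomes measured in all women, under the stated inputs.
- Say that it does not cover mammography, that mammography will be reported as an estimate with a confidence interval, and that a null result there is not an adequately powered test.
- Note that power for the birth control outcome, which Table 5 limits to women without menopause or sterilization, also depends on the number eligible.
- State the single f actually used. If it is 0.12, N=124 and the stated power stand; 0.13 would give about 86-87% and 92%.

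The cost is a few sentences, with no added enrolment or data collection. The plan gives up the claim of adequate power for mammography.

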
organizations (i.e. transitional living facilities, DV shelters, social support centers, etc.)
 
 • Randomize participants to intervention and control arms • Deliver SHE-Women to N~100 women via text-Web platform; deliver standard of care discharge planning session to N~100 women • Conduct baseline, post-intervention, 1, 2, 3 year assessments of women's health literacy and screening/risk reduction outcomes • Conduct N~30 stakeholder interviews to determine efficacy of COVID-19 module 	
 • Screening/risk reduction for cervical, breast cancer, unintended pregnancy, STIs and COVID-19 	
 • Manuscript #2 strategies for recruiting women leaving jails into health promotion interventions in Y3 • Conduct follow-ups for 3 years from intervention during Y1-Y5/ maintain 75-85% follow-up rate • Manuscript #3 effectiveness of SHE-Women at improving women's health literacy in Y3 • Manuscript #4 effectiveness of SHE-Women at improving women's health screening/risk reduction in Y4 • Placement of SHE-Women on NCI Research-Tested Intervention Programs site in Y5 • Manuscript #5 3-year outcomes of interventions in Y5
---	---	--

Aim 3. Understand the role and impact of human interaction in electronic interventions by tracking participants and interviewing key stakeholders.

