Intervention arms and procedures. All women will be mailed a SHE-Women booklet with the intervention content. Electronic women's health literacy intervention procedures (intervention arm). e will deliver the integrated, multimedia electronic women's health literacy intervention arm of SHE-Women in text-Web format for individuals recently released from jail or have recent involvement with the criminal-legal system (2 years). Two health educators will be responsible for delivering content to participants, with an estimated contact time of ~10 hours pushed to participants over approximately a 5-day period. However, because it is a text-Web intervention, accessing content will be dependent on user engagement with the platform. We will measure uptake of the intervention components as it relates to number of minutes of engagement and length of time (total number of days) that all content was accessed. The lead health educator will describe the study and obtain consent from participants. If participants consent, they will immediately be asked to participate in a baseline survey.

For Aim 1 pilot study participants, this will occur over phone or in person in the community. For Aim 2 RCT participants – all of this will occur at the jail at the participant's time of discharge. Participants will be informed that after consent/ after they leave jail, in order to initiate the program, they should contact the health educator through phone, text message, email, or Facebook message. We estimate that we might lose 30% of women between consent and initiation of the community-based intervention, simply because they do not follow-up with us. Thus, in the Aim 1 pilot study we will over-recruit by 15 women; and in the Aim 2 RCT we will over recruit by 60 women, to make up for potential loss to attrition. To improve rates of follow-up, we will also collect multiple points of expected contact information for the participants: phone numbers, addresses for themselves or family members; usual places of hangout; and Facebook handle. That way, if participants don't reach out to us within three days of consent/release from jail, we can contact them.

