Standard of care discharge planning session (control arm). In the Aim 1 pilot study, participants will only access the intervention arm content. In the Aim 2 RCT, participants will be randomized after consent to the intervention or control arm. The women will be offered a 10-page women's health booklet that utilizes SHE-Women content, but in print form. The booklet will provide simple definitions, screening guidelines, and local health resources for age and risk appropriate cervical, breast cancer, unintended pregnancy, and STI prevention. We will collect multiple points of contact information for the participants: phone numbers, addresses for themselves or family members; usual places of hangout; and Facebook handle, for follow-up. Participants in this arm of the intervention will be contacted 5 days after receiving the standard of care intervention for post-assessment. Similar to the intervention arm, we expect to lose 30% of women to follow-up, thus we will over-recruit by about 30% for the RCT, as described above. Participants will be asked to reach out to us 5 days after or we will contact them for follow-up and to complete the post-assessment over the phone or through an electronic link to the survey.

We wish to note that although we call the control arm the "standard of care," in reality there is no standard discharge planning session in the jails we work with; women are sent out the door with their belongings. But we feel it would be grossly unethical to not provide the control arm with some health information, even if limited.

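### The attrition and power figures do not agree with each other: 60% of 200 is 120, not 124; the baseline number is both about 200 and 260; the expected early loss is both 30% and 15%; and the follow-up benchmark leaves out 60 randomised women

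*Combined protocol and SAP*

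**What the plan says.** All references are to the combined protocol and SAP, under APPROACH.

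- **Power.** The section reports that "a sample of 124 women will produce" at least 80% power: 80% for health literacy (three measurements) and 85% for screening/risk reduction (four). Allowing for up to 40% attrition, it sets recruitment at about 200 women at baseline and says power holds "even with a low follow-up rate as small as 60" per cent.
- **Table 4 (Aim 2).** 260 at consent and baseline, 220 at initiation, 200 at post-intervention, then 170, 160 and 150 at years 1, 2 and 3.
- **Intervention arms and procedures.** "We estimate that we might lose 30% of women between consent and initiation of the community-based intervention". The RCT therefore over-recruits by 60.
- **Standard of care discharge planning session (control arm).** "participants will be randomized after consent to the intervention or control arm". This section also expects a 30% loss and over-recruits by about 30%.
- **Table 3, Aim 2 benchmarks.** "maintain 75-85% follow-up rate", for follow-up over three years from the intervention.
- **Power, closing text.** The analysis is intent-to-treat, with multiple imputation for missing data.

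**The concern.** These figures describe one flow of women through one trial, so they should fit together. They fail to do so in four places:

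1. The follow-up floor of 60%, applied to 200, gives fewer women than the power statement needs.
2. The baseline number is about 200 in the power text and 260 in the table beside it.
3. The loss before initiation is 30% in the text and about half that in Table 4, and over-recruiting by 60 does not offset a 30% loss.
4. The follow-up benchmark is counted from women who completed the post-intervention assessment, although randomisation comes earlier.

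At stake are the stated power guarantee and an accurate view of missing data. Under intent to treat, a woman lost between randomisation and post-assessment is missing data. How women enter the programme also differs by arm: intervention women are asked to make contact to start, while control women are followed up five days after receiving their material. Early loss could therefore differ between arms, and a retention rate that starts at post-intervention would not show it.

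**Working it through.** **Inputs.** f = 0.12, because the Power section states "we conservatively assumed the smallest observed effect size of $f=0.12$ for our power calculation"; r = 0.46; t = 3 (health literacy) or 4 (screening/risk reduction); two groups; alpha 0.05 (Data analysis). Counts are from Table 4.

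**Formula.** Repeated-measures ANOVA, group-by-time interaction, noncentral F: λ = f²·N·t/(1 − r), df1 = t − 1, df2 = (N − 2)(t − 1).

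**Reproducing the plan's figure.** For N = 124 and t = 3, λ = 0.0144 × 124 × 3 / 0.54 = 9.92 on 2 and 244 df, giving 80.7% power (plan: 80%). The smallest N reaching 80% is 122, so 124 is reproduced. For t = 4 the result is 87.3% (plan: 85%), close but not exact. The section also lists f = 0.13 for the same run. That value gives 86.9% and 92.4% at N = 124, which does not match the stated powers, so f = 0.12 is used below.

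**1. The 60% floor**

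- 0.60 × 200 = 120, four below 124.
- t = 3: λ = 0.0144 × 120 × 3 / 0.54 = 9.60, power 79.3%.
- t = 4: λ = 0.0144 × 120 × 4 / 0.54 = 12.80, power 86.1%.
- With f = 0.13 and N = 120: 85.7% and 91.4%.
- Follow-up of 200 that leaves 124: 124/200 = 62%. Baseline number that leaves 124 at 60%: 124/0.60 = 206.7, so 207.

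**2. Baseline number**

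About 200 (Power text) against 260 (Table 4; the recruitment section also gives about 260).

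**3. Early loss**

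- Table 4, consent to initiation: 220/260 = 84.6%, a loss of 15%.
- Table 4, consent to post-intervention: 200/260 = 76.9%, a loss of 23%.
- Stated 30% loss: 260 × 0.70 = 182, not 200. Ending with 200 would take 200/0.70 = 286.
- The 60 extra women are 30% of 200 (200 × 1.30 = 260). Adding 30% to the target offsets a 23% loss, not a 30% loss.

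**4. Follow-up by base**

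| Visit | Expected n | Of 200 post-intervention | Of 260 randomised |
|---|---|---|---|
| Year 1 | 170 | 85% | 65% |
| Year 2 | 160 | 80% | 62% |
| Year 3 | 150 | 75% | 58% |

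Of the 110 randomised women expected to lack year-3 data (260 − 150), 60 are lost before post-intervention (260 − 200).

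**Power at the expected counts (f = 0.12, r = 0.46)**

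- Health literacy, last measured at year 1, N = 170, t = 3: λ = 13.6, power 91.8%.
- Screening/risk reduction, last measured at year 3, N = 150, t = 4: λ = 16.0, power 93.2%.

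**The case against.** The strongest reply is that nothing here threatens the trial, and much of it stands.

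- **The benchmark is internally consistent.** It is tied to follow-up after the intervention, and 150/200 and 170/200 are exactly 75% and 85%. A reader might infer that the 75-85% figure is simply wrong. The documents do not support that; what can be criticised is the choice of base in an intent-to-treat trial that randomises after consent.
- **The 60% floor is not breached.** A reader might set 58% at year 3 against the 60% floor. The floor is defined on about 200 women and the 58% on 260. In women, the plan expects 150, above both 120 and 124.
- **The shortfall is small.** It is 0.7 percentage points, for health literacy only, in a worst case described with approximate numbers. Since 122 women already reach 80% at f = 0.12, a floor of 61% (122/200) would do on the power calculation; 62% follows from the plan's own 124.
- **Nothing is concealed.** Table 4 prints every step from 260 to 150, and the over-recruitment is explained in several sections.
- **The 30% is tentative**, and the section on strategies for success allows further recruitment if attrition is higher than expected.
- **The analysed number is not the last-visit count**, because mixed models and multiple imputation are planned.

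These points limit the size of the concern. They do not make 120 equal 124, 200 equal 260, or 30% equal 15%, and they do not bring the 60 women lost early into the follow-up rate.

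**Conclusion.** The concern holds as a set of inconsistent planning figures, together with a follow-up rate counted from the wrong starting point for an intent-to-treat trial. The 60% floor leaves four women fewer than the plan's 124: 79.3% power for health literacy, while screening/risk reduction stays at 86.1%. The stated 30% loss would leave about 182 women at the point where Table 4 has 200. From randomisation, expected follow-up is 65%, 62% and 58%.

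It would be tempting to conclude that the trial is underpowered. The documents do not support this: the expected counts of 170, 160 and 150 all exceed 124, and power on them is 91.8% and 93.2%.

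The power results assume f = 0.12, r = 0.46, sphericity, a continuous outcome and complete cases, as in the plan's type of calculation. The correlation matters more than the four women: at r = 0.25, the lowest baseline-to-year-1 value the plan quotes, 124 women give 65.9% power for health literacy. Even there, 169 women (t = 3) and 144 women (t = 4) reach 80%, within the expected 170 and 150. Treating the 260 as randomised rests on the statement that randomisation follows consent.

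**What to change.** 1. **Power.** Restate the tolerable follow-up as 62% of 200 (124/200), or keep 60% and state about 79% power for health literacy. Use one effect size throughout; f = 0.12 is the one that reproduces 124.
2. **Baseline number.** Use one figure in the Power section, the recruitment section and Table 4. If 260 are consented and randomised, say so, and describe 200 as the number expected at post-intervention.
3. **Early loss.** Make the 30% loss, the over-recruitment of 60 and Table 4 agree. If 30% is kept, expect about 182 rather than 200 and revise the later rows of Table 4. If Table 4 is kept, replace 30% with 15% before initiation and 23% by post-intervention.
4. **Follow-up.** Report it from all randomised women, by arm, and set the benchmark on that base (expected 65%, 62% and 58%). The rate among post-intervention completers can be given as a secondary figure, labelled as such.

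The cost is edited text and one revised table, with no added enrolment.
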